11 SAFETY ANALYSES

All analysis of safety variables will be performed using the SS, unless otherwise stated.

11.1 Extent of exposure

11.1.1 Drug administration

All drug administration details (including date, time of injection, location, side of body and volume delivered) will be listed. The IMP will be given as 2 sc injections at each planned dosing visit (Baseline, Week 4 and Week 16).

11.1.2 Number of injections received

The number of injections received will be summarized by treatment group using descriptive statistics, based on the SS. There are anticipated to be 2 injections per dosing visit, ie, a total of 6 injections for subjects that completed the treatment as planned.

11.1.3 Subject time at risk

The subject time at risk represents the time a subject was at risk for having an AE and will be used to calculate the exposure adjusted incidence rate (EAIR) and exposure adjusted event rate (EAER) as described in [Section 11.2](#).

The subject time at risk (days) will be calculated as follows:

$$\text{Time at risk} = (\text{Date of Last Dose} - \text{Date of First Dose}) + 140 \quad [11]$$

In cases where the last clinical contact or last visit occurs prior to completion of the SFU period, the subject time at risk is calculated as follows:

$$\text{Time at risk} = (\text{Date of Last Contact} - \text{Date of First Dose}) + 1 \quad [12]$$

This will apply for the following:

- For subjects entering the extension study the date of last contact (in PS0016) refers to the date of the visit at which they enter the extension study (ie, Week 20, 24, 28 or 36)
- For subjects that discontinue prematurely (ie, and no SFU data are available), the date of final contact refers to the date of the latest contact with the subject during the study after

which no further information or data are available. This will be reported on the study termination page of the CRF.

- For subjects that have died during the study the date of last contact refers to the date of death
- Subject-years at risk is defined as the subject time at risk divided by 365.25. The days at risk and subject-years at risk will be listed together with the drug administration information (Section 11.1.1).

11.2 Adverse events

11.2.1 Definitions and classification of adverse events

All AEs will be recorded in the CRF from informed consent until study completion or termination.

Adverse events with start date prior to the first administration of IMP are defined as pre-treatment AEs. A TEAE is defined as any AE with a start date/time at the time of or after the first administration of IMP up until the last received dose of IMP + 140 days (which covers the 20 week SFU Period). Adverse events occurring after this date will not be classified as TEAEs and will therefore be excluded from the summary tables.

Where dates are missing or partially missing, AEs will be assumed to be treatment-emergent, unless there is clear evidence to suggest that the AE started prior to dosing. Handling of missing dates/times for classification of AEs as TEAEs is described in Section 4.2.4.

In order to allow for a comparative period across all subjects, prior to the point at which subjects are eligible to enter the extension study, TEAEs will be classified as follows:

- **Treatment Period TEAEs:** all TEAEs with onset at the time of or after the first administration of IMP up until the Week 20 visit. Any TEAEs that occur on the date of the Week 20 visit will be included (ie, the cut off will be assumed to be at 23:59 hours on the date of Week 20). Such TEAEs will be designated as 'Treatment Period' TEAEs in the tabulations. Any subjects that withdraw prior to Week 20 will have Treatment Period TEAEs cut off at 140 days relative to the first dose (ie, equivalent to 20 weeks).
- **Post-Treatment Period TEAEs:** all TEAEs with onset after the Week 20 visit up until the last dose of IMP + 140 days will be designated as 'Post-Treatment' TEAEs in the tabulations. Thus, any tabulation including Post-Treatment TEAEs will include only those TEAEs for subjects not entering the extension study at all or those TEAEs for subjects who enter the extension study at a later visit. For subjects that withdraw prior to Week 20, Post-Treatment Period TEAEs are classified as those starting after 140 days relative to the first dose (ie, equivalent to 20 weeks).

For the EAIR and EAER tabulations the above classifications will not be applicable, as these summaries are, by definition, adjusted for the individual exposure at risk for each subject.

All AEs will be coded and categorized by intensity (mild/moderate/severe) and relationship to IMP (related/not related).

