## 8 STUDY PROCEDURES BY VISIT

Table 5–1 (schedule of study assessments) provides a general overview of study assessments. A list of procedures to be completed at each visit is described below.

- Visit windows of  $\pm 3$  days on either side of the scheduled dosing are permitted; however, the Investigator should try to keep the subjects on the original dosing schedule. The window of  $\pm 3$  days is relative to Baseline and applicable for all subsequent visits. Changes to the dosing schedule outside of the 3-day window must be discussed with the Medical Monitor.
- For the Safety Follow-Up Visit (20 weeks after the last dose), the visit should occur no more than 3 days prior to the scheduled visit date and within 7 days after the scheduled visit date (-3 days/+7 days).

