#### **12.6.1.1 Tuberculosis assessment by IGRA**

During conduct of the study, the TB assessment by IGRA (QuantiFERON TB GOLD is recommended) will be performed at Screening and should be repeated at Week 36/Early

Withdrawal Visit for all subjects. The test results will be reported as positive, negative, or indeterminate. UCB also recommends that a TB specialist be consulted where TB (latent or active) is suspected or if there are doubts regarding test results. If latent or active TB is identified, subject must undergo appropriate study-specified withdrawal procedures. The retest during Screening must be done during the protocol-defined Screening window (up to 4 weeks).

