#### **12.6.5 Physical examination**

The physical examination will include general appearance; ear, nose, and throat; eyes, hair, and skin; respiratory; cardiovascular; GI; musculoskeletal; hepatic; neurological (including limb reflexes); and mental status. Physical examination will be performed at the visits specified in [Table 5–1](#). Findings considered clinically significant changes since the physical examination at the Screening Visit will be recorded as AEs.

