### **14.3.3 Planned safety and other analyses**

#### **14.3.3.1 Safety analyses**

All safety variables will be analyzed for all subjects in the SS.

Adverse events will be coded according to the Medical Dictionary for Regulatory Activities (MedDRA®). Treatment-emergent adverse events (TEAEs) will be summarized descriptively by treatment group, primary system organ class, high level term, and preferred term. Additional tables will summarize TEAEs by intensity and relationship to study drug, TEAEs leading to withdrawal from the study, treatment-emergent SAEs, and deaths.

Treatment-emergent adverse events will be defined as events that have a start date on or following the first administration of study treatment up until the final administration of study treatment +140 days (covering the 20-week SFU Period). To allow for a fair comparison across all subjects, exposure at risk for defining treatment-emergence during the 28-week treatment period will be cut off at the Week 16 Visit (for subjects who complete through the Week 16 Visit) or at 20 weeks (140 days) after the last administration of study treatment (for subjects who discontinue prior to the Week 16 Visit).

Laboratory values, urinary values, ECGs, vital signs, and extent of exposure will be presented descriptively by treatment group.

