11.3 Clinical laboratory evaluations

Laboratory data (clinical chemistry, hematology, and urinalysis) and changes from Baseline (if applicable) for numeric variables will be listed by treatment group and visit. Any laboratory variables with values that are BLQ or ALQ will be handled as described in [Section 4.2.2](#) for calculation of changes from Baseline and for summary tables. Values outside the reference range for the numeric variables will be flagged in the listings and in addition, will be listed separately. The reference ranges will also be reported in the listings.

Clinical chemistry and hematology variables will be summarized by treatment group (including All Subjects) at each visit, for both absolute values and changes from Baseline.

Laboratory variables will be grouped according to the laboratory function panel and categorized as normal, high or low, if applicable, based on the reference range supplied by the analytical laboratory. For selected variables that are identified in [Table 11-1](#), the change in category from Baseline will be presented in shift tables at all post-Baseline visits.

The number and percentage of subjects with treatment-emergent markedly abnormal (TEMA) laboratory results (to match the TEAE definition stated in [Section 11.1.3](#)) will be tabulated by treatment group and visit. Markedly abnormal laboratory values will be defined as those categorized as Grade 3 and above based on the ranges defined as per the Common Terminology Criteria for Adverse Events (CTCAE) Version 4.03 (2016). These are provided in [Table 14-4](#). The tabulation will include a category for the incidence of TEMA results over all visits which will also count unscheduled measurements.

In addition, for absolute neutrophil count (ANC), all grade 2 CTCAE abnormalities ($<1.5 - 1.0 \times 10^9/L$) will be listed separately, with results from all visits for any subject that has any grade 2 abnormality.

Laboratory measurements meeting the criteria for TEMA will be listed separately for hematology and chemistry. The listings will include all measurements for any variable with at least one TEMA result for each subject.

Any additional laboratory variables not included in the outputs described previously will be listed separately. These will include the following:

- Serology
- Pregnancy tests (serum and urine)
- Follicle stimulating hormone (FSH) (only for postmenopausal women)

The results of the Quantiferon TB Gold test will be listed separately.

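### The treatment-emergent window ends at last dose + 140 days, but a compliant Safety Follow-Up Visit may fall as late as day 147, so onsets and markedly abnormal values on days 141 to 147 are left out of the TEAE and TEMA tables

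*SAP*

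**What the plan says.** **AE window.** SAP 11.2.1 classifies AEs by onset: "A TEAE is defined as any AE with a start date/time at the time of or after the first administration of IMP", and "up until the last received dose of IMP + 140 days (which covers the 20 week SFU Period". It then states the consequence: "Adverse events occurring after this date will not be classified as TEAEs and will therefore be excluded from the summary tables". Protocol 14.3.3.1 uses the same limit for the same stated reason: "up until the final administration of study treatment +140 days (covering the 20-week SFU Period". AEs with missing or partial dates are presumed treatment-emergent unless they clearly began before dosing.

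**Visit window.** Protocol section 8 schedules the SFU Visit 20 weeks after the last dose and adds that "the visit should occur no more than 3 days prior to the scheduled visit date and within 7 days after the scheduled visit date". Protocol Table 5–1 and section 8.11 repeat this tolerance.

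**Laboratory and vital signs.** SAP 11.3 plans a table of "The number and percentage of subjects with treatment-emergent markedly abnormal (TEMA) laboratory results", matched to the TEAE definition and limited to CTCAE Grade 3 and above, plus a separate TEMA listing for hematology and chemistry. SAP 11.4.1 does the same for vital signs, where Table 14–6 sets criteria for systolic and diastolic blood pressure only. Both sections cite SAP 11.1.3 for the TEAE definition, but 11.1.3 defines time at risk; the TEAE definition is in 11.2.1.

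**What happens at the visit.** It includes safety laboratory tests, vital signs, an ECG, a physical examination and a TB test. The IGRA "will be performed at Screening and should be repeated at Week 36/Early" Withdrawal. For the examination, "Findings considered clinically significant changes since the physical examination at the Screening Visit will be recorded as AEs".

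**The concern.** The plan justifies its cut-off by saying that it covers the follow-up period, yet the cut-off stops short of the last day on which the follow-up visit is allowed. No SAP rule extends the window to the actual visit date.

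The effect is clearest for measured values, which carry the date of the visit. A Grade 3 laboratory result from a compliant visit on day 139 counts as TEMA; the same result from a compliant visit on day 143 does not. For AEs the exposed part is onset on days 141 to 147. That can include an examination finding with no earlier symptoms, if the site records the visit date as its start.

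With about 45 subjects in two arms, one Grade 3 value or one event of special monitoring visibly changes a table. Whether it counts should not depend on which permitted day the subject attended.

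**Working it through.** **Inputs**
- Treatment-emergent limit: last dose + 140 days (SAP 11.2.1; Protocol 14.3.3.1).
- SFU Visit: 20 weeks after last dose, −3/+7 days (Protocol Table 5–1, sections 8 and 8.11).
- Last planned dose: Week 16, which is 16 × 7 = 112 days after the first dose.
- Time at risk: SAP 11.1.3, equations [11] and [12].
- Planned sample: about 45 subjects.

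**1. The plan's own figure.** 20 × 7 = 140 days. The stated figure is reproduced, and it covers the nominal visit day.

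**2. Permitted visit days.** 140 − 3 = 137 and 140 + 7 = 147, which gives 11 days. Days 137 to 140 (4 days) are inside the window; days 141 to 147 (7 days) are outside. 7/11 = 64% of permitted days. If Week 36 were instead counted from Baseline, with the Week 16 dose 3 days late or 3 days early, the latest in-window visit would fall on day 144 or day 150 after the last dose. The gap remains either way.

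**3. Size of the gap for AE onset.** Follow-up to day 147 is 112 + 147 = 259 days from first dose. The uncovered part is at most 7/259 = 2.7%. If visits were spread evenly over the 11 days, the mean uncovered time would be (1 + 2 + … + 7)/11 = 28/11 = 2.5 days per subject.

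**4. Subjects whose final visit falls after day 140.** The documents give neither the number reaching the visit nor its timing, so both are assumptions here. The table counts attendees, not events.

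| Subjects reaching SFU Visit (assumed) | 10% after day 140 | 64% (even spread) | 100% |
|---|---|---|---|
| 15 | 1.5 | 9.5 | 15 |
| 30 | 3.0 | 19.1 | 30 |
| 45 | 4.5 | 28.6 | 45 |

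**5. Rates.** For a subject dosed on schedule, equation [11] gives 112 + 140 = 252 days, so numerator and denominator stop together. SAP 11.1.3 places subjects who enter the extension at Week 36 under equation [12], which runs to the visit date. Entry on day 147 gives (112 + 147) + 1 = 260 days. Days 141 to 147 are then in the denominator, while SAP 11.2.1 keeps events on those days out of the numerator.

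**6. After the fix.** Maximum time at risk under equation [11] rises from 252 to 259 days (259/252 = 1.028, +2.8%). For 45 subjects the base is 45 × 252/365.25 = 31.0 subject-years, and the addition is at most 45 × 7/365.25 = 0.86.

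**The case against.** **The 20-week period is literally covered, and +7 days is only a scheduling tolerance.** The first half is true. But the protocol treats a day-147 visit as compliant and collects safety data at it, so the tolerance is part of the follow-up that the cut-off is said to cover.

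**Twenty weeks is about five half-lives.** Protocol 6.1 says so in its contraception criterion, and the half-lives in Protocol 2.2.1 agree: 5 × 27.81 = 139 days and 5 × 28.25 = 141 days. Neither document gives this as the reason for the TEAE limit, and these values make day 140 no sharp boundary. In arm A the last dose is placebo at Week 16, so the limit falls 84 + 140 = 224 days after the last bimekizumab dose at Week 4.

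**AEs are cut by onset, not by discovery.** This stands. A reader might infer that whatever is first found at a late visit is lost. It is not: an AE reported on day 145 that began by day 140 is a TEAE, and missing or partial dates are presumed treatment-emergent. How sites date a finding without symptoms is left to completion guidelines outside these documents.

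**Most outputs keep late values.** This also stands. A reader might infer that the findings vanish from the safety tables altogether. ECG summaries, by-visit laboratory and vital-sign summaries, shift tables, TB test and examination listings, and the AE listings have no such limit. The liver table covers any post-Baseline visit, so it apparently keeps them too. Deaths have an overview row for all AEs as well as one for TEAEs. Whether an IGRA conversion alone would enter the opportunistic infection table on any day depends on a sponsor spreadsheet not included here.

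**The TEMA rule is not fully clear.** It tabulates by visit and over all visits, which might suggest that the whole SFU Visit counts, and it cites the wrong section. Read strictly, matching the TEAE definition excludes day 141 onward. The ambiguity is itself a reason to state the end date.

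**Early extension entrants are unaffected.** Agreed: their SFU assessments take place at Weeks 20 to 28, that is 28 to 84 days after a Week 16 dose.

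**Conclusion.** The point holds for a defined set of data. AEs with onset on days 141 to 147 are left out of the TEAE tables, including those for AEs of special monitoring. Grade 3 or higher laboratory values and markedly abnormal blood pressures measured at a compliant SFU Visit on those days are left out of the TEMA tables, and the laboratory values also out of the TEMA listings. The measured values are the more material part; for AEs the gap is at most 7 of 259 days.

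The 64% is a share of permitted days. It might be read as a share of subjects or events, which the documents do not support, since they give no distribution of visit timing. Nor do they support a general claim that exposure-adjusted rates are biased: under equation [11] events and time stop together, and the mismatch is confined to Week 36 extension entrants under equation [12].

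The conclusion assumes that the SFU Visit is scheduled from the last dose and that TEMA follows the definition in 11.2.1. In a descriptive, exploratory study this is a modest correction, but an inexpensive one that should be made.

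**What to change.** - In SAP 11.2.1, end the treatment-emergent window at the later of last dose + 140 days and the date of the in-window SFU Visit, which is at most last dose + 147 days. Carry the same end date into the Post-Treatment Period TEAE rule.
- Apply that end date to the TEMA rules in SAP 11.3 and 11.4.1, and correct their cross-reference from 11.1.3 to 11.2.1.
- Use the same end date for time at risk in equation [11]. For subjects entering the extension at Week 36, make the event numerator end on the date that equation [12] uses.
- Record the change in SAP 3.9, which already explains another departure from the protocol's TEAE rule.

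The cost is a few lines of text and one derivation. The drawbacks are up to 7 more days at risk per subject and a window end that varies slightly with the visit date.

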### **12.2.2 Procedures for reporting serious adverse events**

If an SAE is reported, UCB must be informed within 24 hours of receipt of this information by the site (see contact information for SAE reporting listed in the Serious Adverse Event Reporting section at the front of the protocol). The Investigator must forward to UCB (or its representative) a duly completed "Investigator SAE Report Form for Development Drug" (SAE Report Form) provided by UCB, even if the data are incomplete, or if it is obvious that more data will be needed in order to draw any conclusions. Information recorded on this form will be entered into the global safety database.

An Investigator SAE Report Form will be provided to the Investigator. The Investigator SAE Report Form must be completed in English.

It is important for the Investigator, when completing the SAE Report Form, to include the assessment as to a causal relationship between the SAE and the IMP administration. This insight from the Investigator is very important for UCB to consider in assessing the safety of the IMP and in determining whether the SAE requires reporting to the regulatory authorities in an expedited manner.

Additional information (eg, autopsy or laboratory reports) received by the Investigator must be provided within 24 hours. All documents in the local language must be accompanied by a translation in English, or the relevant information included in the same document must be summarized in the Investigator SAE Report Form.

The Investigator is specifically requested to collect and report to UCB (or its representative) any SAEs (even if the Investigator is certain that they are in no way associated with the IMP), up to 30 days from the end of the study for each subject, and to also inform participating subjects of the need to inform the Investigator of any SAE within this period. Serious AEs that the Investigator thinks may be associated with the IMP must be reported to UCB regardless of the time between the event and the end of the study.

Upon receipt of the SAE Report Form, UCB will perform an assessment of expectedness of the reported SAE. The assessment of the expectedness of the SAE is based on the IB.

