3.9 Changes to protocol-defined analyses

In the clinical study protocol the definition of the FAS included all subjects with a valid measurement of the primary efficacy variable post-Baseline. However, this was adjusted to all subjects with a valid Baseline measurement for the primary efficacy variable in the SAP in order to comply with program standards and FDA requirements (ie, inclusion into the FAS is no longer dependent on availability of post-Baseline data).

According to the final clinical study protocol spaghetti plots of change from Baseline in PASI would be plotted for each subject over time. However as the PASI response is based on percentage change, it was deemed more appropriate to present the individual plots based on percentage change from Baseline.

The protocol stated that exposure at risk for defining treatment-emergence for treatment-emergent adverse events (TEAEs) would be cut off at the Week 16 visit (for subjects who complete through the Week 16 visit) or at 20 weeks (140 days) after the last administration of study treatment (for subjects that discontinue prior to the Week 16 visit). This was further stated to be done in order to provide a fair comparison across all subjects when comparing the incidence of TEAEs. In this SAP amendment it has been clarified that the definition of a TEAE is any AE with onset following the first administration of study medication until the final administration of study medication + 140 days (regardless of study discontinuation). In order to allow for direct comparison of the treatment groups with respect to incidence of TEAEs, prior to the point at which subjects are eligible to enter the extension study, it would be necessary to use a cut off at Week 20 (ie, the first point at which a subject may enter the extension study). This has also been clarified in the SAP amendment accordingly.

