11.2.2 Calculation of exposure adjusted incidence and event rates

The EAIR is defined as the number of subjects (n) with a specific TEAE adjusted for the exposure and will be scaled to 100 subject-years:

$$EAIR = 100 \times \frac{n}{\sum_{i=1}^N T_{Exp,i}} \quad [13]$$

In the above equation, N is the total number of subjects at risk (in each treatment group) and $T_{Exp,i}$ is the time at risk for subject i , expressed in years. Subject time at risk represents the time a subject was at risk for having a TEAE calculated as follows:

- For subjects experiencing the specific TEAE the time at risk ($T_{Exp,i}$) is calculated from the time of the first dose to the onset of the TEAE. If a subject has multiple events, the time at risk is calculated relative to the first occurrence of the TEAE being considered.
- For subjects who do not experience the specific TEAE the total time at risk ($T_{Exp,i}$) is calculated as described in [Section 11.1.3](#).

Exact Poisson 95% CIs (lower confidence limit [LCL], upper confidence limit [UCL]) for the EAIR will be calculated using the relationship between the Poisson and the chi-square distribution (Fay and Feuer, 1997):

$$LCL = \frac{\chi_{2n, \frac{\alpha}{2}}^2}{2}, \quad UCL = \frac{\chi_{2(n+1), 1 - \frac{\alpha}{2}}^2}{2} \quad [14]$$

where n is the number of subjects with the specific TEAE for the incidence rate of interest and is the basis for the number of the degrees of freedom for the chi-square quantile. The LCL and UCL calculated above will be scaled to the number of subject-years by dividing these by the total exposure at risk for each treatment group ($\sum_{i=1}^N T_{Exp,i}$).

The EAER is defined as the total number of TEAEs (including repeat occurrences in individual subjects) divided by the total time at risk scaled to 100 subject-years:

$$EAER = 100 \times \frac{n_{AE}}{\sum_{i=1}^N T_{Risk,i}} \quad [15]$$

where n_{AE} is the total number of TEAEs and $T_{Risk,i}$ is the time at risk for subject i , expressed in years (calculated as described in [Section 11.1.3](#)).

No confidence intervals will be computed for EAER.

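### The TEAE window has no stop at extension entry but time at risk does, so the exposure-adjusted rates can set a few post-entry events against shorter follow-up

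*SAP*

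**What the plan says.** **Numerator.** SAP 11.2.1 runs the TEAE window "up until the last received dose of IMP + 140 days (which covers the 20 week SFU Period". SAP 3.9 repeats it as "until the final administration of study medication + 140 days (regardless of study discontinuation". Neither sentence mentions extension entry.

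**Denominator.** SAP 11.1.3 gives (last dose − first dose) + 140 days (equation 11). It switches to (last contact − first dose) + 1 (equation 12) "In cases where the last clinical contact or last visit occurs prior to completion of the SFU period". For extension entrants, "the date of last contact (in PS0016) refers to the date of the visit at which they enter the extension study".

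**Rates.** In SAP 11.2.2 the EAER divides all TEAEs by the 11.1.3 time. The EAIR uses that time only for subjects without the event. For a subject with it, time at risk "is calculated from the time of the first dose to the onset of the TEAE".

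**Period split.** SAP 11.2.1 divides TEAEs at the Week 20 visit, where "the cut off will be assumed to be at 23:59 hours on the date of Week 20". It says that Post-Treatment tables contain only subjects who do not enter the extension or who enter later, but gives no cut date for those entering at Week 24 or 28. It then states that this split does not apply to the EAIR and EAER.

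**Data capture.** SAP 11.2.1 has adverse events recorded in the CRF until study completion or termination. Under SAP 5.1 an extension entrant completes PS0016 at the entry visit. Protocol 12.2.2 also requires serious events to be collected "up to 30 days from the end of the study for each subject", and Protocol 13.3.1 has serious events entered in the eCRF as well as on the SAE form.

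**Meaning of IMP.** SAP 5.1 applies the term to the first extension dose too. In its disposition listing it limits dose dates to PS0016. Section 11.2.1 carries no such limit.

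**The concern.** A rate per person-time needs events and time to be cut at the same point. Here an entrant's time is cut at entry and the event definition is not. SAP 11.2.1 sets the period split aside for the EAIR and EAER on the ground that they already adjust for exposure, and that holds only if the two cuts agree.

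There is also a question of attribution. The first extension dose is given at the Week 20, 24 or 28 visit itself. An event later that day, if captured, is a PS0016 TEAE. For a Week 20 entrant it also falls in the Treatment Period because of the 23:59 cut-off. SAP 14.6.7 counts hypersensitivity and anaphylactic reactions within 24 hours of any IMP administration and treats an event with no start time on a dosing date as at or after dosing. With IMP not limited to PS0016 doses, a reaction to an extension injection could qualify.

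The tables affected are the Overall, EAIR/EAER and special-monitoring (AESM) tables, and the Treatment Period tables for Week 20 entrants. Incidence of adverse events is the primary safety variable. Entry before Week 36 follows relapse. Arm A has its last active dose at Week 4, so it probably supplies more early entrants; that is an inference, as the documents give no rate.

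**Working it through.** **Inputs.** Last dose at Week 16 = day 112 after first dose. Window of 140 days (SAP 11.2.1). Entry visits at Weeks 20, 24, 28 and 36 = days 140, 168, 196 and 252. Serious-event collection of 30 days (Protocol 12.2.2). Arm A of about 30 subjects (SAP 2.3). The share entering early is not stated, so 10%, 30% and 50% are assumed.

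**The plan's own figure.** 20 × 7 = 140 days, and 112 + 140 = 252 days = Week 36. This agrees with the 20-week follow-up.

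**Window against time at risk.** Time at risk from equation 12 is the entry day + 1. The gap is 252 minus the entry day.

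| Entry | Time at risk (days) | Days of TEAE window after entry | 30 days / time at risk |
|---|---|---|---|
| Week 20 | 141 | 112 | 21.3% |
| Week 24 | 169 | 84 | 17.8% |
| Week 28 | 197 | 56 | 15.2% |
| Week 36 | 253 | 0 | no gap |

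All three gaps exceed 30 days, so the whole 30-day serious-event period lies inside the TEAE window.

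**Arm A as a whole, 30-day route only.** Mean time at risk for entry spread evenly over three visits is (141 + 169 + 197)/3 = 169 days. Subjects who do not enter early contribute 252. With share f entering, the excess is 30f / [252(1 − f) + 169f].

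- f = 0.1: 3 / (226.8 + 16.9) = 1.2%
- f = 0.3: 9 / (176.4 + 50.7) = 4.0%
- f = 0.5: 15 / (126 + 84.5) = 7.1%

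**How each rate goes wrong.** Take a Week 20 entrant with a serious event 20 days after entry. In the EAER the event counts and the subject contributes 141 days, so the event has no matching person-time. In the EAIR that subject contributes 140 + 20 = 160 days to onset, while an event-free Week 20 entrant contributes 141. The fault in the EAIR is unequal censoring: only cases add time after entry.

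**Entry-day events.** The + 1 in equation 12 covers the entry date. These events have person-time, and the only problem is which treatment they are attributed to.

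**The case against.** The strongest reply is that data capture already bounds the numerator. PS0016 records adverse events until completion, and an entrant completes at the entry visit. The visit and follow-up assessments come before the first extension dose, so the last planned adverse event record does too. That stands for most non-serious events. A reader might otherwise infer that all events in the 112, 84 or 56 days count, which under a constant event rate would inflate entrants' EAER by 252/141 = 1.79, 252/169 = 1.49 or 252/197 = 1.28. The documents do not support those ratios as an expected effect.

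The 30-day route is itself uncertain. Whether a serious event after extension dosing is entered in PS0016, in the extension or in both depends on an extension protocol that is not among the documents. The point therefore holds only if such events are captured.

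Other stronger readings also fail:

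- **Last contact or death.** For discontinued subjects without follow-up data, SAP 11.1.3 defines final contact as the point after "which no further information or data are available"; for deaths it is the date of death. There is no gap in either case.
- **The phrase about study discontinuation in 3.9.** It deals with the protocol's separate rule for subjects who discontinue before Week 16. Entrants are completers, so it does not address them. The defect is the missing stop.
- **Extension bimekizumab.** The current text says study treatment or IMP and does not give the regimen.
- **Only relapsers enter.** SAP 2.3 and 5.1 also allow entry after the Week 36 visit.

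The safety tables are descriptive, the EAER has no confidence interval, and SAP 2.4 says that the study is not powered for safety. Stray events could be traced, because the listings flag extension entry and show onset dates. These points limit the harm but do not make the two rules agree.

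**Conclusion.** The mismatch is in the text: the TEAE window and an early entrant's time at risk end on different days, and nothing in 11.2.1 or 11.2.2 aligns them for the EAIR and EAER. The practical reach is narrow. It covers serious events in the 30 days after entry and events on the entry date after the extension dose, each only if it enters the PS0016 data.

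The per-entrant figures of 15% to 21% rest on a Week 16 last dose and full 30-day capture. The Arm A figures of about 1% to 7% rest also on the assumed 10% to 50% entry, evenly spread. Both sets describe serious-event ascertainment time and are not predicted changes in overall adverse event rates. The numerical effect is probably small. The point still merits correction, because a stated rule can give a wrong rate or attribution and the remedy is short.

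**What to change.** Amend SAP 11.2.1 and 3.9 along these lines: a TEAE has onset from the first dose to the earlier of (a) the last PS0016 dose of IMP + 140 days and (b) for subjects entering the extension study, extension entry, taken as the first extension dose on the entry date. State that IMP means PS0016 doses.

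Apply the same stop to:

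- the Week 20 Treatment Period cut-off, for Week 20 entrants;
- the Overall, EAIR/EAER and AESM tables;
- the 24-hour hypersensitivity and anaphylaxis rule in 14.6.7.

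List serious events after extension entry separately and flag them. The days inside the window but outside time at risk then fall from 112, 84 and 56 to 0. Time at risk in 11.1.3 needs no change, and no special rule is needed for subjects who end at last contact.

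**Cost.** SAP wording and one programmed comparison. The date and time of the first extension dose are needed to place entry-day events. The 5.1 disposition listing holds the entry visit but only PS0016 dose times, so either the extension dose time is obtained or the entry visit date serves as a proxy, with a stated rule for events on that date. A few late events move from tables to a listing.
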